9.4 Adverse Events

Treatment-emergent adverse events (TEAEs) are defined as those adverse events (AEs) with onset after the first dose of study drug or existing events that worsened after the first dose during the study. Treatment-emergent AEs will be summarized by treatment group. Partial or missing start or end dates will be imputed per Section 9.1.1.

Verbatim terms on case report forms will be mapped to preferred terms and system organ classes using the latest version of MedDRA.

At Weeks 2, 4, 6, 12, 24, 48 and 52, treatment-emergent adverse events (TEAEs, i.e., AEs occurring during or after treatment initiation) will be summarized in the following tables: all reported TEAEs, all treatment-related TEAEs, severe TEAEs, TEAEs leading to dose interruption, TEAEs leading to dose modification, TEAEs leading to study discontinuation, TEAEs of special interest, and anticholinergic TEAEs. Two sets of the above tables will be produced: (a) for cumulative TEAEs up to the current visit reported by those making the visit, and (b) for cumulative TEAEs up to the current visit reported by all Safety Population subjects (including those absent from the current visit). At each of the 7 indicated weeks, each of the above tables will summarize the subject incidence (frequency count and %) for the specified TEAE, mapped to MedDRA System Organ Class and Preferred Term, according to the highest severity reported. Subjects with only unknown severity for a TEAE will be counted under the severity unknown category. Additionally, serious TEAEs and treatment-related serious TEAEs will be summarized in the same manner for all data through Week 52.

Version: 1.0 Page 26 of 51

Summaries that are displayed by system organ class and preferred terms will be ordered by descending incidence of system organ class in the combined BBI-4000 group and preferred term within each system organ class. The combined BBI-4000 group will not be displayed and will only be used for sorting. TEAEs of special interest include the following:

- Vision blurred
- Mydriasis
- Urinary hesitation
- Pupils unequal

Adverse event data will be presented in data listings by subject, treatment group, and event. Serious TEAEs and TEAEs leading to discontinuation of the study will be presented in separate data listings. Death is not expected. However, should death occur on study, the event will be reported with detailed narratives.

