collected and analyzed at the Screening Visit and at Visit 5 (Week 6), Visit 10 (Week 24), and Visit 16 (Week 48) for routine hematology, chemistry, and urinalysis parameters. Patient-reported outcomes: HDSM-Ax and DLQI will be recorded during the study at predefined time points. Patient Global Impression of Severity (PGI-S) will be administered with each administration of the HDSM-Ax and the Patient Global Impression of Change (PGI-C) will be administered at the 24 Week and 48 Week (EOT) visits. HidroQoL will be recording during the study at baseline, Visit 3 (Week 2), and Visit 5 (Week 6); only the first 100 subjects enrolled will complete this assessment.

A total of 17 scheduled visits will take place over approximately 52 weeks.

Test Product, Dose, and Mode of Administration

5% or 15% sofpironium bromide (BBI-4000) gel topically applied to the axillae

Duration of Treatment

48 weeks (11 months) followed by a 4-week post-treatment visit (52 weeks)

Safety Assessments

- Adverse events
- Local tolerability assessments including burning, itching, dryness, scaling and erythema
- Vital signs (blood pressure, pulse rate, respiratory rate, and temperature)
- Laboratory tests (hematology, chemistry, and urinalysis) and pregnancy testing in FOCBP

Efficacy Assessments

The following assessment measures will be conducted to evaluate the long-term efficacy of sofpironium bromide gel, 5% and 15%:

- HDSM-Ax as measured by the subject
- DLQI as measured by the subject (for subjects ≥ 17 years of age)
- Patient Global Impression Scales; Severity (PGI-S) and Change (PGI-C)

Additionally, HidroQoL assessment will be conducted as an exploratory analysis, as measured by the subject (for subjects \geq 17 years of age). This assessment will be performed at baseline, Visit 3 (Week 2), and Visit 5 (Week 6) for only the first 100 subjects enrolled in the study.

Statistical Methods

Safety Analyses

Treatment emergent adverse event (TEAE) descriptions will be mapped to standard terms, i.e., MedDRA System Organ Class and Preferred Term. At each post-baseline visit, the number and proportion of subjects reporting any given TEAE will be tabulated by severity; each subject will be counted only once according to the worst severity reported up to the current visit. Separate tables will be constructed for (a) all reported TEAEs, (b) protocol treatment-related TEAEs, (c) serious TEAEs, and (d) TEAEs leading to protocol treatment discontinuation.

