Adverse Event Relationships to Study Drug

Outcome

Each AE will be characterized according to the outcomes described in the following table:

SprickellBiotech

Page 39 of 74

Outcome	Description
Recovered/Resolved	The subject has fully recovered from the event with no observable residual effects.
Recovering/Resolving	The effects of the event are improving, or events have stabilized (are constant and not expected to improve or worsen) but have not returned to baseline.
Not recovered/Not Resolved	The effects of the event are still present and changing. The event is not considered stabilized or resolved.
Recovered/Resolved with Sequelae	The subject has fully recovered from the event with some observable residual effects.
Fatal	The event was the primary cause of death (may or may not be the immediate cause of death).
Unknown	The event outcome is unknown.

Death is an outcome of an event and not an event per se. Sudden death or death due to unexplainable cause(s) is to be reported, but follow-up will be pursued until cause of death is determined.

Action Taken with Study Drug

Action taken with study drug in relation to each adverse event will be characterized as follows:

None

Drug withdrawn

Drug interrupted

Unknown

Not applicable

Other (specify on CRF)

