10.3 Safety Analyses

Safety variables are local tolerability assessments, AEs, laboratory evaluations, and vital signs.

At each post-screening visit, local tolerability (burning, itching, scaling, dryness, and erythema at either axilla) will be tabulated by severity. At each post-baseline visit, local tolerability will also be summarized as cumulative shift tables vs. baseline. Subject counts for each symptom will be cross tabulated by baseline severity and the maximum post baseline severity reported for either axilla up to the current visit.

Adverse events will be coded from the verbatim text into preferred term (PT) and primary system organ class (SOC) using the most current version of Medical Dictionary for Regulatory Activities (MedDRA). At each postbaseline visit, treatment-emergent adverse events (TEAEs, i.e., AEs occurring during or after treatment initiation) will be summarized in the following tables: all reported AEs, all treatment-related AEs, all SAEs, and AEs leading to investigational product discontinuation. Three sets of the above tables will be produced at each visit: (a) for TEAEs reported at the current visit by those making the visit, (b) for cumulative TEAEs up to the current visit reported by those making the visit, and (c) for cumulative TEAEs up to the current visit reported by all enrolled patients (including those absent from the current visit). For each TEAE, a patient will appear at most once by the highest severity reported.

Laboratory parameters will be descriptively summarized (mean, SD, median, minimum, maximum) for values at each visit and for changes from screening at each subsequent visit. In addition, at each post-screening visit, parameter status (low, normal, high) will also be summarized as shift tables vs. screening status.

Vital signs will be descriptively summarized (mean, SD, median, minimum, maximum) for values at each visit and for changes from screening at each subsequent visit.

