5. STUDY SUBJECTS

5.1 Disposition of Subjects

Subject disposition will be summarized for all randomized subjects by treatment group. Summaries will include the number and percentage of subjects in each analysis population, reason for exclusion from the PP population, completing treatment, completing the study, and discontinuing the study early by the primary reason for discontinuation. Analysis populations are defined in Section 4. Treatment completers are subjects with "Yes" noted for the question "Did the subject complete treatment?" on the Study Disposition CRF page. Study completers are subjects with "Normal Study Completion" noted for the question "Subject's Status or Primary Reason for Early Termination" on the Study Disposition CRF page. Study discontinuers are subjects with any response to "Subject's Status or Primary Reason for Early Termination" other than "Normal Study Completion" on the Study Disposition CRF page.

All subject disposition data will be listed for all randomized subjects.

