13. CHANGES TO THE ANALYSES PLANNED IN THE PROTOCOL

Analyses specified in the protocol dated 6 May 2019 that have changed in this SAP include the following:

- Protocol Synopsis
 - The synopsis describes the baseline of HDSM-Ax as the average of Screening and Day 0. The baseline definition has been updated to be the Day 1 visit.
- Protocol Section 10.1 Analysis Populations
 - The definition of ITT population has been updated to include all subjects who were randomized.
- Protocol Section 10.2 Endpoints
 - For the exploratory efficacy endpoint, the protocol describes an interim analysis. It has been clarified in this SAP that the interim analysis was not formal and that the treatment groups were not blinded.
 - Endpoints have been added to the 'Other Efficacy Endpoint' section to capture the 11-item total of HDSM-Ax and the 7-item total of HDSM-Ax.
- Protocol Section 10.3 Safety Analysis
 - The protocol describes three sets of AE tables to be produced at each visit. The first set "(a) TEAEs reported at the current visit by those making the visit" will not be generated, as it will not provide any substantial information to the safety profile".
 - The protocol states that all SAEs will be summarized by the three sets of AE tables. Due to an expected low incidence, one SAEs table and one treatment-related SAEs table will be generated for all data through Week 52.

Version: 1.0 Page 33 of 51

Statistical Analysis Plan 24 February 2020

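### The SAP tabulates TEAEs leading to study discontinuation instead of the protocol's TEAEs leading to drug discontinuation, and does not declare the change

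*SAP*

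**What the plan says.** The protocol names the table twice. Section 10.3 lists, among the TEAE tables, "AEs leading to investigational product discontinuation". The synopsis, under Statistical Methods, lists "TEAEs leading to protocol treatment discontinuation".

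SAP 9.4 gives a different set: tables for dose interruption, then "TEAEs leading to dose modification, TEAEs leading to study discontinuation". The listings follow the same line: "Serious TEAEs and TEAEs leading to discontinuation of the study will be presented in separate data listings". SAP Section 17 accordingly has a listing of adverse events resulting in study discontinuation and no counterpart for drug withdrawal.

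SAP Section 13 records departures from the protocol. For Protocol 10.3 it gives two, opening with "The protocol describes three sets of AE tables to be produced at each visit" (one of the three sets is dropped) and "The protocol states that all SAEs will be summarized by the three sets of AE tables" (reduced to two tables through Week 52). The move from drug to study discontinuation is not there.

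Protocol 9.2.1.2 provides a field for drug stopping: "Action taken with study drug in relation to each adverse event will be characterized as follows". Its categories are None, Drug withdrawn, Drug interrupted, Unknown, Not applicable, and Other with a specification.

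**The concern.** Adverse events are a primary endpoint here, and the number of subjects who had to stop the gel because of one is a central tolerability result of a 48-week safety study. Stopping the drug and leaving the study are different events. If only the second is tabulated, a subject whose drug is withdrawn for an adverse event but who stays for further visits may appear in no discontinuation table. The same could happen to a subject whose exit is put down to withdrawal of consent. Protocol 7.4 recognises that possibility: it asks sites to look for an adverse event behind a voluntary withdrawal.

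The change is also undeclared. SAP Section 1 says that changes from the protocol's analyses will be documented in the SAP, so a reader of Section 13 would assume that the protocol's table is still coming.

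There is a smaller, related gap. The SAP plans tables of TEAEs leading to dose modification, but the protocol's action-taken list has no category for reduced dosing and the SAP does not say how such an event is to be identified.

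**Working it through.** No power, alpha or event-rate figure in the plan bears on this. SAP 2.6 states that there was no formal sample size calculation. The check is a count of planned tables, a comparison of sections, and an illustration.

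**1. Count of planned tables.** SAP 9.4 names 7 time points (Weeks 2, 4, 6, 12, 24, 48, 52), 8 TEAE categories and 2 sets of subjects (those making the visit; all Safety Population subjects).

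- Expected cumulative tables: 7 × 8 × 2 = 112.
- SAP Section 15, numbers 14.3.1.4.1 to 14.3.1.10.16: 7 blocks of 16 = 112. The two agree.
- Dose interruption: 7 × 2 = 14. Dose modification: 14. Study discontinuation: 14. Drug or treatment discontinuation: 0.

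**2. Are the two events the same in these documents?**

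- SAP 5.1 takes treatment completion from one CRF question ("Treatment completers are subjects with" a Yes to that question) and study completion from another, which records a single primary reason for early termination.
- SAP Section 7, Table 1, has a frequency for drug withheld by the investigator, with dosing multiplier 0. A subject can therefore be on study without drug.
- Protocol 8.1.4 says that subjects who do not respond to interruption or concomitant therapy *can* have drug withdrawn and be discontinued. Section 7.4 says that a subject *may* be discontinued. Only confirmed pregnancy (Section 9.5.1) makes study exit mandatory.

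So the two events are expected to coincide often, but nothing makes them coincide for adverse events in general.

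**3. Can the protocol's table be produced?** Yes. Protocol 9.2.1.2 has the action taken recorded for every adverse event, and Drug withdrawn is one of the categories. That list has no study-exit category, and SAP 9.4 does not say which variable defines a TEAE leading to study discontinuation.

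**4. Illustration of size.** Let n be the arm size, p the true proportion of subjects with an AE-related drug stop, and f the share of those not recorded as an AE-related study exit. Then

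tabulated count = n × p × (1 − f).

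The planned n is 100 (5% gel) and 200 (15% gel), from Protocol Section 2 and SAP 2.3. The documents give neither p nor f. The values below are assumptions.

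| Arm | Assumed p | True count | Tabulated, f = 0 | Tabulated, f = 25% | Tabulated, f = 50% |
|---|---|---|---|---|---|
| 5% gel, n = 100 | 2% | 2 | 2 | 1.5 | 1 |
| 5% gel, n = 100 | 10% | 10 | 10 | 7.5 | 5 |
| 15% gel, n = 200 | 2% | 4 | 4 | 3 | 2 |
| 15% gel, n = 200 | 10% | 20 | 20 | 15 | 10 |

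One missed subject changes the rate by 1/100 = 1.0 percentage point or 1/200 = 0.5 point. A table built on Drug withdrawn would show the true count whatever the value of f.

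**The case against.** The strongest reply is that in this trial the two events are nearly the same. Protocol 8.1.4 mentions drug withdrawal and study discontinuation together, and Section 7.4 lists inability to tolerate the product as a ground for leaving the study. No section describes a route for stopping drug for an adverse event and staying on. The separate CRF questions may exist only because treatment ends at Week 48 and the study at Week 52. The SAP names no source variable, so the study-discontinuation tables might be built from the AE action field after all. The data are not lost either: all adverse events are listed, and the overall TEAE summary (Table 14.3.1.1), whose content is not given, might show drug withdrawals. All of this stands as a limit on the size of the problem. It does not restore the protocol's table or explain why Section 13 omits the change.

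The second reply concerns versions. The SAP follows Amendment 4 (6 May 2019), while the protocol supplied is Amendment 01. SAP Table 1 includes divided-dose frequencies that Amendment 01 Section 8.1.4 does not contain, so dosing rules, and perhaps the action-taken categories, may have changed. For the table of drug discontinuations this carries less weight: Section 13's account of the three table sets matches Amendment 01 Section 10.3, which suggests that the section was largely kept. It does not prove that the list of categories was kept.

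Two stronger readings are tempting and are not supported.

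- A reader might infer that dose modification cannot be recorded on the AE form. It can: the category Other takes a specification, and SAP Section 7 says that the Dosing CRF page collects protocol-indicated modifications. What is missing is a rule that turns these into a TEAE leading to dose modification.
- A reader might take the roughly 2.0% in the protocol's Risk to Subjects text, expect 2 of 100 and 4 of 200 stops, and conclude that one missed case loses 50% or 25% of the count. That 2.0% covers anticholinergic effects only, comes from prior studies of at most 42 days where a duration is stated, and itself counts people who left studies. It cannot size an undercount of 48-week drug withdrawals.

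**Conclusion.** The point holds as a reporting gap. The protocol's table of TEAEs leading to product discontinuation is missing from SAP 9.4, Section 15 and the listings. A study-discontinuation table stands in its place, and Section 13 does not say so. An AE-related drug stop in a subject who stays on study, or whose exit carries another primary reason, may go uncounted.

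The documents do not show that any undercount will occur, and its size cannot be calculated from them. It is zero if every AE-related drug stop is also recorded as an AE-related study exit. Otherwise it equals the share that is not. The conclusion assumes that Amendment 4 kept the protocol's drug-discontinuation table and the Drug withdrawn category, and that Table 14.3.1.1 does not already report drug withdrawal. The dose-modification issue is secondary: a missing derivation rule. The change should be made because the omitted result belongs to the primary objective and its data source already exists.

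**What to change.** In SAP 9.4, Section 15 and Section 17, restore a table and a listing of TEAEs with action taken Drug withdrawn for all Safety Population subjects, at minimum cumulative through Week 52. Keep the study-discontinuation tables as a supplement and name the variable that defines them. Record in Section 13 how the discontinuation tables differ from Protocol 10.3.

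As a secondary clarification, state the source for TEAEs leading to dose modification: the AE action Other with its specification, an AE-linked change of prescribed frequency on the Dosing CRF, or both. Check the Amendment 4 action-taken categories first. No change to the AE form is needed.

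The minimum cost is one table and one listing from data already collected, plus a derivation rule. Repeating the table at all 7 time points for both sets of subjects would add 7 × 2 = 14 tables, which is not necessary to close the gap.

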- If for any reason per the Investigator's or the Sponsor's judgment, discontinuation is in the subject's best interest.
- If the subject becomes pregnant.

Subjects who discontinue the study prior to the completion of all treatment visits will be asked to complete the evaluations corresponding to Visit 16 (Week 48, End of Treatment). The Sponsor will be notified of early discontinuation as soon as possible during the study.

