9.2.1.1 Documentation and Monitoring Adverse Events

All AEs encountered during the clinical trial following subject consent through the last dose of study drug will be recorded on the appropriate Adverse Events case report form (eCRF).

Special considerations:

Elective procedures or routinely scheduled treatments are not considered AEs. However, an untoward medical event occurring in association with a prescheduled elective procedure should be recorded as an AE.

A baseline condition is not considered an AE unless the condition worsens following study drug administration.

Death itself is not considered an AE; it is, instead, the outcome of an AE.

SAEs that are considered related (i.e., determined to be possibly, probably, or definitely related) to sofpironium bromide by the Investigator or Sponsor should be followed until the event resolves or stabilizes (see Section 9.3.1).

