9.4 Follow-up of Adverse Events and Laboratory Test Abnormalities

AE information will be collected during the clinical trial from the time the subject signs informed consent through the final study visit. SAEs that are considered related to study drug by the Investigator or Sponsor should be followed until the events resolve or stabilize.

9.5 **Pregnancy Reporting**

Sexually active females of childbearing potential (FOCBP)* must have a negative pregnancy test prior to study enrollment and must use an effective method of contraception during the course of the study, in a manner such that risk of failure is minimized. Prior to study enrollment, FOCBP must be advised of the importance of avoiding pregnancy during trial participation and the potential risk factors for an unintentional pregnancy. The subject must sign an informed consent form documenting this discussion.

FOCBP must agree to periodic pregnancy testing and use a medically acceptable method of contraception while receiving protocol-assigned product. This includes perimenopausal women who are <12 months from their last menses. Acceptable contraceptive methods include the following:

- Abstinence for the duration of the study or where partner is sterile (e.g., vasectomy) is acceptable form of contraception;
- Hormonal contraception, including oral, injectable, or implantable methods started ≥2 months prior to screening; OR
- Two forms of non-hormonal contraception, including IUD (≥1-week status post placement), or properly used barrier methods (e.g., male or female condoms, cervical cap/diaphragm, spermicidal agents).

* FOCBP for this study includes any premenopausal female capable of becoming pregnant who has not undergone successful surgical sterilization (hysterectomy, bilateral tubal ligation [\geq 6 months prior to baseline] or bilateral oophorectomy) or is not postmenopausal (defined as amenorrhea \geq 12 consecutive months in women \geq 55 years of age).

Subjects who become sexually active or begin to have relations with a partner who is not sterile during the trial must agree to use an effective form of birth control for the duration of the study.

9.5.1 *Time period for collecting pregnancy information*

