9.3 Extent of Exposure

Extent of exposure to study treatment will be summarized for the Safety Population by treatment group. The duration of exposure will be presented in days and summarized using descriptive statistics. Drug (pump) dispensation will be provided in a listing, to include total drug delivered per subject. Each pump will be primed, then weighed, prior to dispensing pumps to subjects. Each pump will be weighed upon return. Total drug delivered will be calculated as the total weight of all pumps dispensed minus the total weight of all returned pumps.

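### TEAEs are shown as crude percentages on two denominators, and both can read below the 48-week risk if subjects leave early for mixed reasons; a censored estimate for key categories would be a cheap addition

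*SAP*

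**What the plan says.** SAP 9.4 tabulates eight TEAE categories at Weeks 2, 4, 6, 12, 24, 48 and 52. In each, "each of the above tables will summarize the subject incidence (frequency count and %) for the specified TEAE", by system organ class, preferred term and highest severity.

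The denominators are set out as follows:
- Set (a): "Two sets of the above tables will be produced: (a) for cumulative TEAEs up to the current visit reported by those making the visit". The table list in SAP 15 labels this set as subjects reaching the given week.
- Set (b): "b) for cumulative TEAEs up to the current visit reported by all Safety Population subjects (including those absent from the current visit".

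Serious events get one cut only: "serious TEAEs and treatment-related serious TEAEs will be summarized in the same manner for all data through Week 52". Follow-up is described on its own in SAP 9.3: "The duration of exposure will be presented in days and summarized using descriptive statistics". It is not linked to the TEAE tables.

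Neither SAP 9.4 nor any table or figure title in SAP 15 and 16 names a person-time rate, a Kaplan-Meier curve or a competing-risk estimate for TEAEs. Two sources could not be checked: the table specifications, which SAP 1 places in a separate document, and the content of Table 14.3.1.1, known only by its title.

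Two protocol statements on the adverse-event window also bear on any such estimate. Protocol 9.2.1.1 has: "All AEs encountered during the clinical trial following subject consent through the last dose of study drug will be recorded". Protocol 9.4 has: "AE information will be collected during the clinical trial from the time the subject signs informed consent through the final study visit".

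**The concern.** Long-term safety is the primary objective, and SAP 3.1 plans no hypothesis tests. The displayed percentages are therefore the main adverse-event result. The design allows up to 300 enrolled to obtain about 150 completers, so substantial attrition is within its own plan.

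A crude percentage handles early leavers in one of two ways. Set (b) keeps them in the denominator as if they had been observed event-free to the end, which lowers the figure when they left for unrelated reasons. Set (a) drops them, which lowers the figure when they left because of the event. A reader might expect the two sets to bracket the true risk. They do not when both kinds of leaving occur: both can then be low, and by similar amounts, so their agreement would look reassuring. If retention differed between the 5% and 15% arms, set (b) could also show a dose difference where there is none.

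**Working it through.** **The plan's own figures.** No event rate or dropout rate is stated, so there is no calculated result to reproduce. The counts agree with each other: 150/300 = 50% completing, and 1:2 allocation gives 100 and 200 enrolled with 50 and 100 completers. The 50% is a design ceiling, not a forecast.

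**Assumed inputs.** True 48-week risk p = 20%, with constant onset unless stated. R is overall retention at Week 48. A fraction f of subjects with the event leave because of it, at the event. All other leaving has a constant hazard and is independent of the event.

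**Formulas.**
- Retention from other causes: s = R / [(1 − p) + p(1 − f)].
- Over 48 weeks, event hazard L = −ln(0.8) = 0.2231 and other-cause hazard M = −ln(s).
- Set (a) at Week 48 = p(1 − f) / [(1 − p) + p(1 − f)].
- Set (b) at Week 48 = L/(L + M) × (1 − 0.8s).
- Life table on the planned weeks (0, 2, 4, 6, 12, 24, 48): per interval q = d / (n − w/2), where n is event-free and present at the start, d first events and w withdrawals; risk = 1 − product of (1 − q).

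**Numbers put in.**
- R = 0.5, f = 0: s = 0.5, M = 0.6931. Set (b) = 0.2435 × 0.600 = 14.6%; set (a) = 20.0%.
- R = 0.5, f = 0.1: s = 0.5/0.98 = 0.510, M = 0.6729. Set (b) = 0.2490 × 0.5918 = 14.7%; set (a) = 0.18/0.98 = 18.4%.
- R = 0.5, f = 0.3: s = 0.5/0.94 = 0.532, M = 0.6313. Set (b) = 0.2612 × 0.5745 = 15.0%; set (a) = 0.14/0.94 = 14.9%.
- R = 0.8, f = 0: s = 0.8, M = L. Set (b) = 0.5 × 0.36 = 18.0%; set (a) = 20.0%.

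| Retention | Leave because of event | Set (a) | Set (b) | Life table |
|---|---|---|---|---|
| 50% | 0% | 20.0% | 14.6% | 19.8% |
| 50% | 10% | 18.4% | 14.7% | 19.8% |
| 50% | 30% | 14.9% | 15.0% | 19.9% |
| 80% | 0% | 20.0% | 18.0% | 20.0% |
| 80% | 30% | 14.9% | 18.5% | 20.0% |

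If leaving is only event-driven (s = 1), set (b) is correct at 20%.

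**Against sampling error.** The standard error of set (b) is √[q(1 − q)/N], with q the displayed proportion. At 80% retention and f = 0 the shortfall is 2.0 points, against 2.7 (N = 200) and 3.8 (N = 100). At 50% it is 5.4 points, against 2.5 and 3.5.

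**When it matters** (50% retention, f = 0). At Week 12, set (b) shows 5.0% against a true 5.4%; at Week 24, 9.0% against 10.6%. For the same 20% risk at Week 48, set (b) shows 19.2% if onset falls in Weeks 0–6 and 12.0% if it falls in Weeks 24–48.

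**Unequal arms.** With 45% and 65% retention (hypothetical), f = 0 and the same 20% risk, set (b) shows 14.0% and 16.4%.

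**Would a person-time rate do instead?** Only under constant hazard. For the same 20% risk, going from full to 50% retention moves the rate per 100 patient-years from 26.8 to 35.4 with onset in Weeks 0–6, and from 22.9 to 18.9 with onset in Weeks 24–48.

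**The case against.** The plan does not ignore attrition. It shows each by-week category on two denominators at seven time points, as Protocol 10.3 had specified, and set (a) is correct when leaving is unrelated to the event. The SAP never calls set (b) a 48-week risk; as an observed proportion of all treated subjects it is valid. Subject listings of adverse events and exposure are planned, and SAP 1 allows supplementary analyses after lock. All of this stands, and it is why the point is minor.

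The inputs are also chosen. The documents' only related figure is about 2.0% of earlier subjects stopping for anticholinergic effects (Protocol 1, Risk to Subjects). Against a 20% risk that is 2/20 = 10% of affected subjects, where set (a) is only 1.6 points low. Those studies, where a treatment period is stated, ran at most 42 days, so the figure does not settle what happens over 48 weeks.

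A reader might also infer that several rules are unsettled. The documents support little of that:
- SAP 9.1.1 does state how missing onset dates are imputed.
- Early leavers "will be asked to complete the evaluations corresponding to Visit 16 (Week 48, End of Treatment" (Protocol 7.4), which could suggest they count as Week 48 attenders. The label for subjects reaching Week 48 in SAP 15 largely answers this.
- The two adverse-event windows conflict in the supplied protocol, which is Amendment 01. The SAP follows Amendment 4, so the conflict may not survive. SAP 9.4 tabulates to Week 52, in line with collection to the final visit.

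What remains is that neither planned set estimates 48-week risk when both kinds of leaving occur, and no estimate that does so is named.

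**Conclusion.** The concern holds as a minor presentation gap. At 50% retention and an assumed 20% risk, set (b) is about 5 points low. Set (a) ranges from correct to about 5 points low as the share leaving because of the event rises from 0 to 30%. At 80% retention with unrelated dropout the shortfall is 2.0 points, within one standard error in either arm. It is small for early-onset events and early visits, and matters mainly from Week 24 with heavy attrition or unequal retention.

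A reader might infer that the plan will understate long-term risk by about a quarter, or that SAP 9.4 contains an error. The documents support neither. They state no dropout or event rate, the two sets are clearly labelled, and set (a) is a real partial safeguard. The absence of a censored estimate is established only for the SAP text and listed titles. The calculations rest on an assumed risk, assumed onset patterns and other-cause leaving that is independent of the event.

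**What to change.** Keep both planned sets. Add, by arm, a Kaplan-Meier or competing-risk (Aalen-Johansen) cumulative incidence with 95% CI at Weeks 24 and 48 for three categories: anticholinergic TEAEs, TEAEs of special interest and TEAEs leading to discontinuation.

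State with it:
- **Censoring rule.** Say what is censored and what, if anything, is a competing event. If all leaving were treated as a competing event, with everyone else followed to Week 48, the estimate would simply return set (b). Leaving for unrelated reasons therefore has to be censored.
- **At-risk window.** Match it to the adverse-event collection period, after reconciling Protocol 9.2.1.1 with Protocol 9.4 against the amendment that the SAP cites.
- **Early-termination visits.** Censor subjects whose early-termination visit is done as Visit 16 at their actual date, not at Week 48.

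Exposure-adjusted rates are optional. If shown, they need a note that they track 48-week risk only under constant hazard.

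The cost is SAP wording and a few table shells; onset dates and exposure are already collected. The estimate is more variable: in 1,500 simulated trials at n = 200, 50% retention and 30% event-driven leaving, its SD was about 3.3 points, against 2.5 for set (b). It still assumes that the remaining dropout is non-informative, and that should be stated beside the result.
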